### **Imputation Procedures**

There are about 3% of subjects with intermittent missing in post-baseline ACR data. Those missing data will be imputed with data estimated from all observed data using the Markov Chain Monte Carlo procedure such that the missing data pattern is monotonic.

The post-treatment ACR data increased gradually over time from the end-of-treatment data. Therefore, a “copy control” strategy will be applied and the imputation model will be fit sequentially at each visit using non-missing data in the placebo arm and any preceding visits (O’Kelly and Ratitch 2014, Section 7.4.2). The estimates of the model parameters are then used to parameterize a Bayesian posterior distribution. At each imputation, missing data in both active and placebo arms will be replaced with predicted values randomly drawn from the distribution. The imputed data will also be applied to the models of subsequent visits. For example, the imputation model at week 26 will be fit using baseline and covariate data (see Section of Imputation Model) and week 26 data of the placebo arm. The ACR data that are missing at week 26 in both active and treatment arms will be imputed in the same way. Similarly, the imputation model for week 52 will utilize observed data of control arm at week 52 and all the preceding data points, whether imputed or observed.

For subjects with missing data, the imputed data up to the earlier of death date or GTED will be combined with observed data. For subjects completing the treatment or developing progression, only data imputed for intermittent missing will be added back to the observed data.

### **Re-construction of time to progression data**

The time to progression will be re-defined based on the imputed dataset where subjects with imputed or observed ACR that met the progression criteria will be considered having events at the corresponding visit. Subjects remaining event-free will be censored at the last scheduled visit before death date or GTED, whichever is earlier.

### **Analysis summary**

The imputed data will be re-analyzed using the same Cox model for the primary analysis (see Section 4.1.2). The imputation process will be repeated 1000 times and the multiple versions of analysis results will be combined into single inferential summary using Rubin’s rule.

## 4.2. Secondary Efficacy Endpoints

### 4.2.1. Definition

There are 2 secondary efficacy endpoints specified in this study:

- The composite endpoint of death from CV causesa or hospitalization for heart failure;
- Death from CV causes (CV Death).

Analyses will be using adjudicated events and adjudication of these outcomes by the Endpoint Adjudication Committee (EAC) will be done in a blinded fashion.

### 4.2.2. Analysis Methods

The analyses will be using the ITT analysis set.

#### 4.2.2.1. The Composite of CV Death or Hospitalization for Heart Failure

The analysis will be based on time to the first occurrence of the composite event using ITT analysis set. The hazard ratio of canagliflozin compared to placebo and its 95% CI will be estimated using a stratified Cox proportional hazards regression model with treatment as the explanatory variable and history of CV disease (secondary and primary prevention) as the stratification factor. The p-value from the stratified log rank test for the treatment effect will also be reported.

The subgroup analysis will be conducted using the same approaches described in Section 4.1.3 and the following subgroups:

- Age group: <65, ≥65 years old;
- Sex: Male, Female;
- Race: White, Black or African American, Asian, Other;
- Region: Central/South America, Europe, North America, Rest of the World;
- Baseline BMI categories (<30, ≥30 kg/m^2);
- Baseline composite blood pressure categories ([SBP <140 or DBP <90 mmHg] vs. [SBP ≥140 and DBP ≥90 mmHg]);
- Baseline eGFR categories (30 to <60, 60 to <90, ≥90 mL/min/1.73m^2);
- Baseline HbA1c ≥ 8%: Yes/No;
- Duration of diabetes ≥ 10 years: Yes/No;
- History of CV disease: Yes/No;
- History of peripheral vascular disease: Yes/No;

---

a Undetermined death is considered CV death.

- History of amputation: Yes/No;
- Baseline use of statin;
- Baseline use of anti-thrombotics;
- Baseline use of RAAS inhibitor;
- Baseline use of Beta blocker;
- Baseline use of insulin;
- Baseline use of diuretics.

[figure not shown]

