1.2. Overall Rationale and Goals for the Study

Patients with T2DM have an increased risk of both microvascular and macrovascular complications which lead to morbidity and mortality. A key issue in patients with T2DM is the potential for hyperglycemia to lead to progressive damage to the kidney. Early on, this damage is reflected by microalbuminuria that may progress to macroalbuminuria and eventually loss of renal function. Hyperglycemia, possibly through production of advanced glycation end products (Diabetes Control and Complications Trial [DCCT]; [Brownlee 2001](#)) and systemic hypertension (DCCT) are known to be risk factors for the onset and progression of diabetic nephropathy. By virtue of its improvement in glycemic control, which has been shown to reduce albuminuria progression in prior studies ([ADVANCE 2008](#); [DCCT 1993](#); [UKPDS 1998](#)), and effects to reduce blood pressure, canagliflozin may slow the progression of diabetic nephropathy.

Hyperglycemia increases glucose levels delivered to the proximal tubule, which is reabsorbed, predominantly via an SGLT-2-dependent mechanism ([Vallon 1999](#)). Increased proximal tubule resorption of glucose results in increases in the proximal tubule reabsorption of sodium and reduces the delivery of sodium to the distal tubule. Decreases in sodium levels in the distal tubule reduce macula densa-dependent tubuloglomerular feedback, which results in afferent glomerular arteriole vasodilation and increases in glomerular pressure ([Vallon 1999](#)). Increases in glomerular pressure are believed to be an important factor in the onset and progression of diabetic nephropathy ([Anderson 1986](#); [American Diabetes Association \[ADA\] 2004](#)). ACEI and ARB decrease glomerular pressure by stimulating efferent glomerular arteriole vasodilation and reduce albuminuria and the progression of diabetic nephropathy (IDNT, [Lewis 2001](#), and RENAAL, [de Zeeuw 2004](#)).

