4.2. Inclusion Criteria

Potential subjects must satisfy all of the following criteria to be enrolled in the study:

Inclusion Criteria at Screening Visit

- Man or woman with a diagnosis of T2DM with HbA_{1c} level $\geq 7.0\%$ to $\leq 10.5\%$ at screening and be either (1) not currently on AHA therapy or (2) on AHA monotherapy or combination therapy with any approved agent: eg, sulfonylurea, metformin, pioglitazone, alpha-glucosidase inhibitor, GLP-1 analogue, DPP-4 inhibitor, or insulin.
- History or high risk of CV events defined on the basis of either:
 - Age ≥ 30 years with documented symptomatic atherosclerotic CV events: including stroke; MI; hospital admission for unstable angina; coronary artery bypass graft; percutaneous coronary intervention (with or without stenting); peripheral revascularization (angioplasty or surgery); symptomatic with documented hemodynamically-significant carotid or peripheral vascular disease; or amputation secondary to vascular disease.
 - Age ≥ 50 years with 2 or more of the following risk factors determined at the screening visit: duration of T2DM of 10 years or more, systolic blood pressure >140 mmHg (average of 3 readings) recorded at the Screening Visit, while the subject is on at least one blood pressure-lowering treatment, current daily cigarette smoker, documented

micro- or macroalbuminuria (see Section 3.2, Study Design Rationale, for definition) within one year of screening, or documented HDL-C of <1 mmol/L (<39 mg/dL) within one year of screening.

Note: An overall target ratio of approximately 70%:30% for CV history (first category):risk factors (second category) will be implemented (with a maximum of approximately 40% in the second category). This target is intended to be a global ratio and may vary by region. The proportion of subjects in these categories will be monitored centrally.

Note: the term “documented” in the above paragraphs refers to the required information being clearly noted in hospital/clinical records or in physician-referral documents, copies of which should be retained in the subject’s study files.

- Women must be:
 - postmenopausal, defined as
 - >45 years of age with amenorrhea for at least 18 months, or
 - >45 years of age with amenorrhea for at least 6 months and less than 18 months and a known serum follicle stimulating hormone (FSH) level >40 IU/L, or

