## **4. EFFICACY**

The analysis will be performed based on the ITT analysis set, if not otherwise specified.

All statistical tests, except those for the primary and secondary efficacy endpoints, will be considered nominal and reported with a 2-sided 95% confidence level.

Unless otherwise stated, all efficacy analyses and summaries will be performed using the treatment groups assigned by IWRS.

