#### **4.1.3. Subgroup Analyses**

The homogeneity of treatment effect on the occurrence of the primary endpoint across subgroups will be examined (at a 2-sided significance level of 0.05) via a test for the treatment by subgroup interaction by adding this term and the subgroup as covariates (treated as class variables) to the primary efficacy analysis (Section 4.1.2) model. Subgroup analysis will be conducted when the total number of events is greater than 10 for two treatment groups (all canagliflozin group and placebo) and at least 1 event in both groups. Factors exhibiting interactions at a significance level of  $p < 0.05$  will be identified as suggesting treatment effect heterogeneity, recognizing the multiplicity in testing multiple subgroups such that one or more p-values  $< 0.05$  may be expected to be observed by chance alone.

If a significant interaction is observed, the Gail-Simon test will be used to further examine the nature of the interaction (qualitative or quantitative).

The hazard ratio of canagliflozin (all canagliflozin group) compared to placebo and its 95% confidence interval will be estimated for each of the following subgroups:

- Age group:  $<65, \geq 65$  years old;
- Sex: Male, Female;

- Race: White, Black or African American, Asian, Other;
- Region: Central/South America, Europe, North America, Rest of the World;
- Baseline BMI categories ( $<30$ ,  $\geq 30$  kg/m^2);
- Baseline composite blood pressure categories ([SBP $<140$  or DBP $<90$  mmHg] vs. [SBP  $\geq 140$  and DBP  $\geq 90$  mmHg]);
- Baseline eGFR categories (30 to  $<60$ , 60 to  $<90$ ,  $\geq 90$  mL/min/1.73m^2);
- Baseline HbA1c  $\geq 8\%$ : Yes/No;
- Baseline albuminuria: Normoalbuminuria, Microalbuminuria;
- Duration of diabetes  $\geq 10$  years: Yes/No;
- History of CV disease: Yes/No;
- Baseline use of Renin angiotensin aldosterone system (RAAS) inhibitor: Yes/No.

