#### **Imputation model**

Assuming that after treatment discontinuation, subjects discontinued from the canagliflozin arm will exhibit a response similar to subjects in the placebo arm, the imputation model will be fit using the non-missing data in the placebo group and adjusted for covariates that may be related to the missing data mechanism and the risk of progression based on clinical judgment. The potential covariates include:

- Baseline ACR (continuous);
- Baseline eGFR categories (30 to <60, 60 to <90,  $\geq 90$  mL/min/1.73m^2);
- Baseline blood pressure (SBP<140, DBP<90 mmHg): Yes/No;
- Baseline HbA1c  $\geq 8\%$ : Yes/No;
- Age group: <65,  $\geq 65$  years old;
- Race: White, Other;
- Sex: Male, Female;

In case of convergence issues, the covariates will be removed from the model in the descending order of the list (ie, starting from the bottom of the list).

Due to the highly skewed data of ACR, both baseline and post baseline ACR in the imputation model will be log transformed.

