#### **4.2.2.2. CV Death**

The analysis will be based on time to the first occurrence of CV death using ITT analysis set. The hazard ratio of canagliflozin compared to placebo and its 95% CI will be estimated using a stratified Cox proportional hazards regression model with treatment as the explanatory variable and history of CV disease (secondary and primary prevention) as the stratification factor. The p-value from the stratified log rank test for the treatment effect will also be reported.

Subgroup analyses will be performed using the same subgroups and the analysis methods described in Section 4.2.2.1.

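### Should the blood-pressure subgroup count a subject as raised when only one of the two pressures is above its cut-off?

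*SAP*

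**What the plan says.** SAP 4.1.3 (Subgroup Analyses, primary endpoint) lists "Baseline composite blood pressure categories" among its factors, with the same cut-offs and connectives as SAP 4.2.2.1, where the entry reads "Baseline composite blood pressure categories ([SBP <140 or DBP <90 mmHg] vs. [SBP ≥140 and DBP ≥90 mmHg". SAP 4.2.2.2 carries the split to CV death: "Subgroup analyses will be performed using the same subgroups and the analysis methods described in Section 4.2.2.1".

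SAP 4.1.3 also sets a minimum size: "Subgroup analysis will be conducted when the total number of events is greater than 10 for two treatment groups", with at least one event in each arm. SAP 4 gives the standing of these tests: "All statistical tests, except those for the primary and secondary efficacy endpoints, will be considered nominal".

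Baseline blood pressure is handled differently in three other places:
- The imputation model in SAP 4.1.4.3 has, among its potential covariates, "Baseline blood pressure (SBP<140, DBP<90 mmHg): Yes/No".
- The baseline summary in SAP 3.2 uses systolic pressure alone, cut at 140 mmHg.
- Protocol 4.2 counts as one entry risk factor "systolic blood pressure >140 mmHg (average of 3 readings) recorded at the Screening Visit", in a subject on blood-pressure treatment, with no diastolic condition.

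**The concern.** A reader who sees a higher blood-pressure category may take it to mean raised blood pressure in general. Under this rule it means that both pressures are raised. Isolated systolic elevation goes to the lower group. That includes subjects who entered on the systolic risk factor and still have a systolic pressure of at least 140 with a diastolic pressure below 90 at baseline. No passage gives a reason for the rule. If the comma in the imputation covariate means that both pressures are below their cut-offs, subjects with one raised pressure fall on the other side there. Together these suggest a slip in the connectives.

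At stake would be the interpretability and precision of one interaction test. Blood pressure is a relevant modifier for a renal endpoint: Protocol 1.2 says that hyperglycemia and systemic hypertension "are known to be risk factors for the onset and progression of diabetic nephropathy". A small higher group would make the interaction estimate imprecise and, for CV death above all, might leave too few events for the minimum-event rule.

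**Working it through.** **1. The logic of the split.** The two cut-offs give four cells.

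| SBP | DBP | SAP subgroup | Connectives exchanged | Imputation flag, if both must be below |
|---|---|---|---|---|
| <140 | <90 | lower | lower | Yes |
| <140 | ≥90 | lower | higher | No |
| ≥140 | <90 | lower | higher | No |
| ≥140 | ≥90 | higher | higher | No |

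The SAP rule places every subject with both readings in exactly one group. The negation is correct in both sections. A single mistyped connective would normally leave overlapping or incomplete categories, and neither occurs.

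**2. Precision of the interaction test.** The plan states no figure that depends on this split, so there is none to reproduce. With 1:1 arms, D events and a share q of events in the higher group,

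SE(log ratio of HRs) = 2/√(D·q·(1−q)).

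D = 693 comes from Protocol 11.2. The documents give no blood-pressure distribution, so q is assumed. The grid is bivariate normal: SBP mean 130-142 and SD 14-18, DBP mean 74-82 and SD 9-11, correlation 0.3-0.7 (1,080 combinations). Events fall in proportion to subjects unless stated.

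- Higher group as written: 1.8-21.3% of subjects. Exchanged: 24.3-62.4%.
- Ratio of SEs, as written to exchanged: 1.21-3.30.
- With event rates 1.5 times as high if one pressure is raised and 2.25 times if both are: 0.966-2.59, above 1 in 1,067 of 1,080 sets.
- With rates 2 and 4 times as high: 0.82-2.16, above 1 in 834 sets.

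The written rule is usually less precise, but how often and by how much depends on event shares that the documents do not give.

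**3. Power, by where the effect lies.** Write q_b for the both-raised share and q_e for the share with at least one raised. Giving both rules the same ratio of 0.7 yields 10-49% as written against 52-65% exchanged, but the two rules compare different groups, so the same true effect appears as a different ratio under each.

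*Effect confined to both-raised subjects.* The written rule sees log 0.7. The exchanged rule sees (q_b/q_e)·log 0.7, because its higher group is diluted.

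*Effect in all subjects with at least one raised.* The exchanged rule sees log 0.7. The written rule sees log 0.7·(1−q_e)/(1−q_b), because its lower group contains affected subjects.

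Example with SBP mean 137 and SD 16, DBP mean 77 and SD 10, correlation 0.5: q_b = 0.076 and q_e = 0.446.
- SE as written = 2/√(693×0.076×0.924) = 0.287. SE exchanged = 2/√(693×0.446×0.554) = 0.153. Log 0.7 = −0.357.
- Both-raised effect: as written −0.357, power 24%. Exchanged −0.357×0.076/0.446 = −0.061, power 7%.
- At-least-one effect: as written −0.357×0.554/0.924 = −0.214, power 12%. Exchanged −0.357, power 65%.

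Over the whole grid (two-sided 0.05):

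| True ratio of 0.7 lies in | As written | Exchanged | Better rule |
|---|---|---|---|
| both-raised subjects only | 10-49% | 5-17% | as written, all 1,080 sets |
| all with at least one raised | 6-25% | 52-65% | exchanged, all 1,080 sets |

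**4. The minimum-event rule.** If it is applied per category, the higher group needs at least 11 events. Total events required are 11/share: from 11/0.2132 = 52 to 11/0.0179 = 615 as written, and from 11/0.6244 = 18 to 11/0.2429 = 46 exchanged. Even the worst case, 615, is below the 693 planned for the primary endpoint. No secondary event counts are given.

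**The case for a change.** The strongest case for acting is that clarification costs almost nothing before unblinding, whereas regrouping afterwards would look driven by the data. On the assumed grid, 18-53% of subjects would change group, so the two rules are far from interchangeable. The other blood-pressure definitions in the documents do not follow the both-raised rule, and a report reader could misread the category.

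What stands is the description: the rule isolates combined elevation, and no reason is given. But the SAP gives no reason for its cut-offs at age 65, BMI 30 or HbA1c 8% either. The imputation entry is one of several potential covariates, its comma is not explicit, and a covariate that predicts missing ACR values need not match a subgroup boundary. The entry criterion concerns screening systolic pressure and says nothing about how to form an effect-modification subgroup. The risk of post hoc regrouping is met by the rule already being written down. Mixing is not avoided by exchanging the words: that higher group would pool isolated with combined elevation. For a sparse secondary endpoint, the minimum-event rule is the plan's own safeguard.

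**Conclusion.** No change follows. The grouping is complete, mutually exclusive and stated consistently, and analysts can apply it as written. The choice between a both-raised and an at-least-one-raised group is a fair trade-off: each has more power in every assumed set when the effect lies where that grouping looks. Neither can be called better without knowing the blood-pressure distribution, the event shares and the clinical question intended. If the both-raised rule is meant, adding a rationale would alter no result.

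The reach is one nominal factor (1 of 12 for the primary endpoint, 1 of 18 for each secondary endpoint), in a section that already warns that interaction p-values below 0.05 may arise by chance. The primary and secondary tests, alpha and study power do not depend on it. The comma in the imputation covariate is a small gap that a programmer would sensibly read as both below, and it affects only a supportive missing-data analysis. The power figures rest on assumed normal distributions, 693 events spread in proportion to subjects, and a ratio of hazard ratios of 0.7. They show that the ranking reverses and are not estimates for this trial.

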#### **4.2.2.2. CV Death**

The analysis will be based on time to the first occurrence of CV death using ITT analysis set. The hazard ratio of canagliflozin compared to placebo and its 95% CI will be estimated using a stratified Cox proportional hazards regression model with treatment as the explanatory variable and history of CV disease (secondary and primary prevention) as the stratification factor. The p-value from the stratified log rank test for the treatment effect will also be reported.

Subgroup analyses will be performed using the same subgroups and the analysis methods described in Section 4.2.2.1.

### **4.3. Multiplicity Adjustment**

Per the SAP of the integrated summary of CANVAS and CANVAS-R studies, only one alpha family is proposed for the testing of the multiple hypotheses based on the integrated data and the CANVAS-R data. The Type I error for these tests will be strictly controlled via a gatekeeping procedure. If the MACE and the mortality endpoints in the integrated analysis succeed in rejecting the null hypotheses, all of the alpha for testing (ie, 5%) will pass to the CANVAS-R for testing of the primary and the secondary hypotheses of the study. Tests for CANVAS-R hypotheses will proceed sequentially conditional on the statistical significance of the hypothesis tests in the integrated summary at the 5% significant level.

**Figure 3: Hypothesis Testing Sequence**

#### 4.4. Exploratory Efficacy Endpoints

##### 4.4.1. Definition

The following exploratory endpoints will be analyzed:

- Time to the first occurrence of composite endpoint of 40% decrease in eGFR, renal deatha or requirement for renal replacement therapy;
- Time to the first occurrence of composite endpoint of doubling of SCr, renal death or requirement for renal replacement therapy;
- Time to the first occurrence of composite endpoint of 40% decrease in eGFR, renal death, requirement for renal replacement therapy or CV death;
- Time to the first occurrence of composite endpoint of doubling of SCr, renal death, requirement for renal replacement therapy or CV death;
- Time to the first occurrence of composite endpoint of 40% decrease in eGFR, conversion to macroalbuminuria, renal death or requirement for renal replacement therapy;
- Time to the first occurrence of composite endpoint of doubling of SCr, conversion to macroalbuminuria, renal death or requirement for renal replacement therapy;
- Regression of albuminuria;

Regression of albuminuria is the development of normoalbuminuria in a subject with baseline microalbuminuria or macroalbuminuria or the development of microalbuminuria in a subject with baseline macroalbuminuria, accompanied by a decrease in the ACR value of greater than or equal to 30% from baseline. If the ACR at a visit meets the definition of potential regression described above, a confirmatory ACR collection approximately 1 to 2 months later

a Non-CV death with a renal proximate cause is considered as renal death.

(or sooner under unusual circumstances, eg, subject is stopping study drug), should be done. In cases where a confirmatory sample is not collected within 1 to 2 months, the next available set of ACR measurements can be used for confirmation.

- Change in urinary ACR over time;
- Change in eGFR from baseline to the last off-drug measurement;
- Estimated eGFR slopes using all on-drug measurements;
- Changes in HbA1c.
- AHA utilization

